### Estimation of $P_{IA}$

$P_{IA}$  = proportion of RSV events (of total over season) estimated to have been observed at time of early IA

**Attachment 3: Respiratory Viruses Used to Define Coinfections**

The following respiratory viruses will be evaluated by the GenMark Respiratory Panel:

- Influenza A
- Influenza A H1
- Influenza A H3
- Influenza A 2009 H1N1
- Influenza B
- Respiratory Syncytial Virus A
- Respiratory Syncytial Virus B
- Parainfluenza Virus 1
- Parainfluenza Virus 2
- Parainfluenza Virus 3
- Human Metapneumovirus
- Human Rhinovirus
- Adenovirus B/E
- Adenovirus C

The following respiratory viruses will be evaluated by the GeneXpert Respiratory Panel:

- Influenza A
- Influenza B
- Respiratory Syncytial Virus
- SARS-COV-2

The following bacteria will be evaluated by the DDL assay:

- Streptococcus pneumoniae
- Staphylococcus aureus
- Haemophilus influenzae
- Moraxella catarrhalis
- Legionella pneumophila/longbeachae
- Mycoplasma pneumoniae
- Chlamydia pneumoniae
- Bordetella pertussis
- Bordetella parapertussis

#### Attachment 4: Area Under the Curve Calculation

In the calculation of the AUC, not only the date, but also the timing (the real hours, minutes and seconds as captured in the database should be used, but the AUC result should be reported in hours), of the assessment, is taken into account.

$$AUC \text{ of total score} = \sum_{i=2}^T \frac{[TS_{t_i} + TS_{t_{(i-1)}}]}{2} [t_i - t_{(i-1)}] \quad (1)$$

where

$t_i$  = (actual) timepoint  $i$

$t_{i-1}$  = (actual) timepoint ( $i - 1$ )

$T$  = last timepoint

$t_1$  = first timepoint

$TS_{t_i}$  = Total score at (actual) timepoint  $i$

$TS_{t_{(i-1)}}$  = Total score at (actual) timepoint ( $i - 1$ )

**Attachment 5: Therapeutic Interventions of Interest****Corticosteroids prescription**

ATC codes	ATC Text
A01AC	Corticosteroids for local oral treatment
A07EA	Corticosteroids acting locally
C05AA	Corticosteroids
D01AC	imidazoles/triazoles in combination with corticosteroids (subset of terms with this ATC code)
D07	CORTICOSTEROIDS, DERMATOLOGICAL PREPARATIONS
D07A	CORTICOSTEROIDS, PLAIN
D07AA	Corticosteroids, weak (group I)
D07AB	Corticosteroids, moderately potent (group II)
D07AC	Corticosteroids, potent (group III)
D07AD	Corticosteroids, very potent (group IV)
D07B	CORTICOSTEROIDS, COMBINATIONS WITH ANTISEPTICS
D07BA	Corticosteroids, weak, combinations with antiseptics
D07BB	Corticosteroids, moderately potent, combinations with antiseptics
D07BC	Corticosteroids, potent, combinations with antiseptics
D07BD	Corticosteroids, very potent, combinations with antiseptics
D07C	CORTICOSTEROIDS, COMBINATIONS WITH ANTIBIOTICS
D07CA	Corticosteroids, weak, combinations with antibiotics
D07CB	Corticosteroids, moderately potent, combinations with antibiotics
D07CC	Corticosteroids, potent, combinations with antibiotics
D07CD	Corticosteroids, very potent, combinations with antibiotics
D07X	CORTICOSTEROIDS, OTHER COMBINATIONS
D07XA	Corticosteroids, weak, other combinations
D07XB	Corticosteroids, moderately potent, other combinations
D07XC	Corticosteroids, potent, other combinations
D07XD	Corticosteroids, very potent, other combinations
D10AA	Corticosteroids, combinations for treatment of acne
G01B	ANTIINFECTIVES/ANTISEPTICS IN COMBINATION WITH CORTICOSTEROIDS
G01BA	Antibiotics and corticosteroids
G01BC	Quinoline derivatives and corticosteroids
G01BD	Antiseptics and corticosteroids
G01BE	Sulfonamides and corticosteroids
G01BF	Imidazole derivatives and corticosteroids
H02	CORTICOSTEROIDS FOR SYSTEMIC USE
H02A	CORTICOSTEROIDS FOR SYSTEMIC USE, PLAIN
H02B	CORTICOSTEROIDS FOR SYSTEMIC USE, COMBINATIONS
H02BX	Corticosteroids for systemic use, combinations
M01BA	Antiinflammatory/antirheumatic agents in combination with corticosteroids

R01AD	Corticosteroids
R03AK	Adrenergics in combination with corticosteroids or other drugs, excl. anticholinergics
R03AL	Adrenergics in combination with anticholinergics incl. triple combinations with corticosteroids
R03BA	Corticosteroids for inhalation
S01BA	Corticosteroids, plain
S01BB	Corticosteroids and mydriatics in combination
S01CA	Corticosteroids and antiinfectives in combination
S01CB	Corticosteroids/antiinfectives/mydriatics in combination
S02B	CORTICOSTEROIDS
S02BA	Corticosteroids
S02C	CORTICOSTEROIDS AND ANTIINFECTIVES IN COMBINATION
S02CA	Corticosteroids and antiinfectives in combination
S03B	CORTICOSTEROIDS
S03BA	Corticosteroids
S03C	CORTICOSTEROIDS AND ANTIINFECTIVES IN COMBINATION
S03CA	Corticosteroids and antiinfectives in combination

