#### **4.10. Therapeutic Interventions**

The following are considered as therapeutic interventions of interest:

- New/increased bronchodilator/nebulizer treatment
- New/increased corticosteroid prescription
- New/increased antibiotic prescription
- New/increased antiviral prescription

These will be taken from the concomitant medication pages of the eCRF based on [Attachment 5](#).

The ones linked to an ARI or complication of an ARI will be displayed.

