### **5.9.1. Analysis Methods**

The PPE set will be used to analyze the therapeutic interventions. A similar analysis to derive VE as in the first RSV season, limited to any RSV ARI, will be repeated for the second and third RSV season and across season two and three and all three RSV seasons.

The different subcategories of new therapeutic interventions will be summarized only across the three RSV seasons, for participants with any RT-PCR confirmed RSV disease and RT-PCR-confirmed RSV-mediated LRTD based on Case Definition 1.

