### **Bronchodilator/nebulizer treatment**

ATC Code	ATC Text
R03	Drugs for Obstructive Airway Diseases
R03A	Adrenergics Inhalents
R03AA	Alpha-and beta-adrenoreceptor agonists
R03AB	Non Selective beta-adrenoreceptor agonists
R03AC	Selective beta-2-adrenoreceptor agonists
R03AH	Combinations of adrenergics
R03AK	Adrenergics and other drugs for obstructive airway diseases
RO3AL	Adrenergics in combination with corticosteroids or other drugs excl. anticholinergics
R03B	Other Drugs for Obstructive Airways Diseases, Inhalents
R03BA	Glucocorticoids
R03BB	Anticholinergics
R03BC	Antiallergic agents excl. corticosteroids
R03BX	Other Drugs for Obstructive Airways Diseases, Inhalents
R03C	Adrenergics for systemic use
R03CA	Alpha-and beta-adrenoreceptor agonists
R03CB	Non Selective beta-adrenoreceptor agonists
R03CC	Selective beta-2-adrenoreceptor agonists
R03CK	Adrenergics and other drugs for obstructive airway diseases
R03D	Other Systemic Drugs for Obstructive Airways Disease
R03DA	Xanthines
R03DB	Xanthines and Adrenergics

R03DC	Leukotriene receptor agonists
R03DX	Other Systemic Drugs for Obstructive Airways Disease

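### The corticosteroid list in SAP Attachment 5 takes in ATC codes R03AL and R03AK whole, although by their own descriptions both also cover products without a corticosteroid

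*SAP*

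**What the plan says.** SAP Section 4.10 names four therapeutic interventions of interest, one of which is "New/increased corticosteroid prescription". For their source it says: "These will be taken from the concomitant medication pages of the eCRF based on" Attachment 5. The code lists in that attachment are therefore the working definition of each category.

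Three rows of the corticosteroid table matter here:

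- R03AL: "Adrenergics in combination with anticholinergics incl. triple combinations with corticosteroids"
- R03AK: "Adrenergics in combination with corticosteroids or other drugs, excl. anticholinergics"
- D01AC: "imidazoles/triazoles in combination with corticosteroids (subset of terms with this ATC code")

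Only D01AC, of these three, carries a note limiting it to part of the code.

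On use of the categories, Section 4.10.1 leaves season 1 analyses of the subcategories optional, with or without VE. Section 5.9.1 is firmer: "The different subcategories of new therapeutic interventions will be summarized only across the three RSV seasons". It specifies this for participants with any confirmed RSV disease and for those with LRTD under Case Definition 1.

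**The concern.** A code list that defines a drug category should select the products the category is named for. R03AL and R03AK do not do so on the wording printed beside them. Each is a mixed class, and the table takes each one whole. A programmer following the table would flag every product under the two codes as a corticosteroid, and the note on D01AC would encourage that reading, since a restriction appears there and not on the other two rows.

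At stake is the meaning of one exploratory subcategory. A reader of the corticosteroid row in the three-season table would take it as the number of participants who needed a steroid for an RSV illness. It could include participants who received only a steroid-free combination.

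**Working it through.** The SAP gives no figure on this point, so the check is a comparison of rows followed by a trace to the outputs.

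**1. What the two codes contain, on the SAP's own text.** The R03AL description names adrenergic/anticholinergic combinations as the class and adds that triple combinations with a corticosteroid are included. If every member contained a corticosteroid, the addition would be pointless, so the class has members with and without one. The R03AK description allows a corticosteroid or another drug as the partner, so it too has members with and without one. No outside ATC source is needed for either reading.

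**2. How the table handles a mixed code elsewhere.** For D01AC the table gives the code, names the steroid-containing combinations, and notes that only a subset of terms is meant. The plan thus already has a notation for the problem; it is absent from R03AL and R03AK.

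**3. Which participants are affected.** Section 4.10.1 tabulates proportions of participants, and takes its definition of new interventions from Section 4.1.4: a medication absent at baseline, or one with an increased dosage under Attachment 9. Section 4.10 adds that the intervention must be linked to an ARI or its complication. Among participants with the RSV outcome in question, let

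- *a* = those with at least one new or increased, ARI-linked product that does contain a corticosteroid;
- *b* = those with none of these, but with a new or increased, ARI-linked, steroid-free product under R03AL or R03AK.

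The list as written reports *a* + *b*. The intended count is *a*. The relative overstatement is (*a* + *b* − *a*)/*a* = *b*/*a*. A participant who also received a genuine new steroid is in *a* already and adds nothing to *b*. A product taken at baseline with no dose increase adds nothing either. The SAP gives neither *a* nor *b*, so *b*/*a* cannot be computed or bounded.

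**4. Which outputs are reached.**

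| Output | Status in the SAP | Affected? |
|---|---|---|
| Corticosteroid subcategory, three seasons (5.9.1) | Planned summary | Yes |
| Corticosteroid subcategory, season 1 (4.10.1) | Optional, VE optional | Yes, if done |
| Any new therapeutic intervention and its VE (4.10.1, 5.9.1) | Planned | No |
| Primary and secondary endpoints | Planned | No |

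The third row is unaffected because the bronchodilator list contains the parent codes R03 and R03A. A new product under R03AL or R03AK is therefore a therapeutic intervention whether or not it is also flagged as a corticosteroid.

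**5. The descriptions in the bronchodilator list.** There the R03AL row reads "Adrenergics in combination with corticosteroids or other drugs excl. anticholinergics", which, apart from a comma, is the corticosteroid table's text for R03AK. The R03AK row reads "Adrenergics and other drugs for obstructive airway diseases", which differs from its text in the corticosteroid table. The two lists therefore disagree on both codes. Both codes are bronchodilators under either label, so no count changes.

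**The case against.** The strongest reply is that little depends on this. The subcategory is exploratory, the overall intervention measure does not move, the same list applies to both arms, and the intention to restrict mixed codes is inferred from a single annotated row. All of that is fair, and it limits the importance of the point. It does not make the list right: the category is named for corticosteroids and the codes, by their own descriptions, reach beyond them.

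A reader might also infer more than the SAP supports:

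- *That a planned VE is distorted.* Section 5.9.1 commits to VE for new interventions overall and to a summary of the subcategories; it states no VE for the latter. In Section 4.10.1 a subcategory VE is optional.
- *That double counting with the bronchodilator category is itself an error.* The lists overlap elsewhere: R03BA is in both the corticosteroid and bronchodilator lists, and D07C in both the corticosteroid and antibiotic lists. The categories are evidently not meant to be exclusive. The fault is flagging a product that contains no steroid, not flagging a product twice.
- *That the bronchodilator row for R03AL, which appears with a letter O in place of the zero, would lose those products.* The character may come from text extraction (a similar confusion appears as J0IFF in the antibiotic list), and the parent codes R03 and R03A cover the products anyway.
- *That the conflicting descriptions cause the misclassification.* They do not. Only the unrestricted rows in the corticosteroid list can do that.
- *That the overstatement can be given as a percentage.* Any figure would only restate assumed counts of users.

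**Conclusion.** The corticosteroid list is wrong as written for R03AL and R03AK. A participant whose only new or increased, ARI-linked product that the list picks up is a steroid-free member of either code would be counted as having a new corticosteroid prescription. The committed output at risk is the corticosteroid line of the three-season subcategory summary; the season 1 subcategory analysis is at risk if it is carried out.

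The overstatement is *b*/*a* as defined above. It is zero if no such participant exists, and the SAP does not allow it to be estimated. The conclusion rests on two assumptions: that Attachment 5 is applied literally, code by code, and that the category is meant to hold steroid-containing products only, as its name and the D01AC note suggest. This is a low-priority correction.

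**What to change.** In the corticosteroid list of Attachment 5, mark R03AK and R03AL '(subset of terms containing a corticosteroid)', following the D01AC row. Fix the list of coded terms that qualify under the two codes before the analysis is run. As an editorial change with no effect on counts, give R03AK and R03AL the same descriptions in the bronchodilator list as in the corticosteroid list.

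The cost is a short edit to one attachment and a review of the coded terms under two ATC codes. No data collection, endpoint definition or model changes.

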### **Bronchodilator/nebulizer treatment**

ATC Code	ATC Text
R03	Drugs for Obstructive Airway Diseases
R03A	Adrenergics Inhalents
R03AA	Alpha-and beta-adrenoreceptor agonists
R03AB	Non Selective beta-adrenoreceptor agonists
R03AC	Selective beta-2-adrenoreceptor agonists
R03AH	Combinations of adrenergics
R03AK	Adrenergics and other drugs for obstructive airway diseases
RO3AL	Adrenergics in combination with corticosteroids or other drugs excl. anticholinergics
R03B	Other Drugs for Obstructive Airways Diseases, Inhalents
R03BA	Glucocorticoids
R03BB	Anticholinergics
R03BC	Antiallergic agents excl. corticosteroids
R03BX	Other Drugs for Obstructive Airways Diseases, Inhalents
R03C	Adrenergics for systemic use
R03CA	Alpha-and beta-adrenoreceptor agonists
R03CB	Non Selective beta-adrenoreceptor agonists
R03CC	Selective beta-2-adrenoreceptor agonists
R03CK	Adrenergics and other drugs for obstructive airway diseases
R03D	Other Systemic Drugs for Obstructive Airways Disease
R03DA	Xanthines
R03DB	Xanthines and Adrenergics

R03DC	Leukotriene receptor agonists
R03DX	Other Systemic Drugs for Obstructive Airways Disease

**Antibiotic prescription**

ATC Code	ATC Text
A01AB	Antiinfectives and antiseptics for local oral treatment
A02BD	Combinations for eradication of Helicobacter pylori
A07A	Intestinal antiinfectives
D06	Antibiotics and chemotherapeutics for dermatological use
D07C	Corticosteroids, combinations with antibiotics
D09AA	Ointment dressings with antiinfectives
D10AF	Antiinfectives for treatment of acne
G01	Gynecological antiinfectives and antiseptics
J01	Antibacterials for systemic use
J01A	Tetracyclines
J01AA	Tetracyclines
J01B	Amphenicols
J01BA	Amphenicols
J01C	Beta-Lactam Antibacterials, penicillins
J01CA	Penicillins with extended spectrum
J01CE	Beta-lactamase sensitive penicillins
J01CF	Beta-lactamase resistant penicillins
J01CG	Beta-lactamase inhibitors
J01CR	Combinations of penicillins, incl. beta-lactamase inhibitors
J01D	Other Beta-Lactam Antibacterials
J01DB	First generation cephalosporins
J01DC	Second generation cephalosporins
J01DD	Third generation cephalosporins
J01DE	Fourth generation cephalosporins
J01DF	Monobactams
J01DH	Carbapenems
J01DI	Other cephalosporins and penems
J01E	Sulfonamides and Trimethoprim
J01EA	Trimethoprim and derivatives
J01EB	Short acting sulfonamides
J01EC	Intermediate-acting sulfonamides
J01ED	Long-acting sulfonamides
J01EE	Combinations of sulfonamides and trimethoprim, incl derivatives
J01F	Macrolides, Lincosamides and Streptogramins
J01FA	Macrolides
J01FG	Streptogramins

J01G	Aminoglycoside Antibacterials
J01GA	Streptomycins
J01GB	Other aminoglycosides
J01M	Quinolone Antibacterials
J01MA	Fluoroquinolones
J01MB	Other quinolones
J01R	Combinations of antibacterials
J01RA	Combinations of antibacterials
J01X	Other Antibacterials
J01XA	Glycopeptide antibacterials
J01XB	Polymyxins
J01XC	Steroid antibacterials
J01XD	Imidazole derivatives
J01XE	Nitrofurans derivatives
J01XX	Other Antibacterials
J0IFF	Lincosamides
R02AB	Antibiotics
S01A	Antiinfectives
S01AA	Antibiotics
S01AB	Sulfonamides
S02A	Antiinfectives
S02AA	Antiinfectives
S02C	Corticosteroids and antiinfectives in combination
S02CA	Corticosteroids and antiinfectives in combination
S03	Antiinfectives
S03AA	Antiinfectives
S03C	Corticosteroids and antiinfectives in combination
S03CA	Corticosteroids and antiinfectives in combination

### **Antiviral prescription**

ATC Codes	ATC Text
D06BB	Antivirals
J05	Antivirals for systemic use
J05A	Direct acting anti-virals
J05AA	Thiosemicarbazones
J05AB	Nucleosides and nucleotides exc. Reverse transcriptase inhibitors
J05AC	Cyclic amines
J05AD	Phosphonic acid derivatives
J05AE	Protease inhibitors
J05AF	Nucleosides and nucleotides reverse transcriptase inhibitors

---

J05AG	Non-nucleoside reverse transcriptase inhibitors
J05AH	Neuraminidase inhibitors
J05AP	Antivirals for treatment of HCV infections
J05AR	Antivirals for treatment of HIV infections
J05AX	Other antivirals
S01AD	Antivirals

**Attachment 6: Binomial Exact Test**

$$\begin{aligned}
 \text{Vaccine Efficacy} &= 1 - \text{Relative Risk} = 1 - \frac{\# \text{ of Events}_{VX} / \# \text{ of Subjects}_{VX}}{\# \text{ of Events}_P / \# \text{ of Subjects}_P} \\
 &= 1 - \frac{1}{r} * \frac{\# \text{ of Events}_{VX}}{\# \text{ of Events}_P} = 1 - \frac{1}{r} * \frac{\# \text{ of Events}_{VX} / \# \text{ of Events}_T}{(\# \text{ of Events}_T - \# \text{ of Events}_{VX}) / \# \text{ of Events}_T} \\
 &= 1 - \frac{1}{r} * \frac{\# \text{ of Events}_{VX} / \# \text{ of Events}_T}{1 - \# \text{ of Events}_{VX} / \# \text{ of Events}_T} = 1 - \frac{p}{r * (1 - p)}
 \end{aligned}$$

Where,

$$r = \frac{\# \text{ of Subjects}_{VX}}{\# \text{ of Subjects}_P}$$

$$p = \# \text{ of Events}_{VX} / \# \text{ of Events}_T$$

**# of EventsVX** = number of events in the Ad26. RSV. preF group

**# of EventsP** = number of events in the Placebo group

**# of EventsT** = number of events, regardless the group

Therefore, there is a monotonic link between VE, the vaccine efficacy, and p, the proportion of subjects in the vaccine group among the total cases in the two groups.

Note that, conditional on the total number of events, **# of EventsVX** is binomially distributed (**# of EventsVX, n**) with n the expected proportion of events in the vaccine group under the true vaccine efficacy.

The CI for vaccine efficacy can then be derived from the exact CI from p (Dragalin, Fedorov and Chevart, 2002).

### Attachment 7: Lawton-Brody Instrumental Activities of Daily Living (Lawton-Brody IADL Scale)

LAWTON – BRODY INSTRUMENTAL ACTIVITIES OF DAILY LIVING SCALE (IADL)			
Scoring: For each category, circle the item description that most closely resembles the client's highest functional level (either 0 or 1).			
A. Ability to Use Telephone		E. Laundry	
1. Operates telephone on own initiative-looks up and dials numbers, etc.	1	1. Does personal laundry completely	1
2. Dials a few well-known numbers	1	2. Launders small items-rinses stockings, etc.	1
3. Answers telephone but does not dial	1	3. All laundry must be done by others	0
4. Does not use telephone at all	0		
B. Shopping		F. Mode of Transportation	
1. Takes care of all shopping needs independently	1	1. Travels independently on public transportation or drives own car	1
2. Shops independently for small purchases	0	2. Arranges own travel via taxi, but does not otherwise use public transportation	1
3. Needs to be accompanied on any shopping trip	0	3. Travels on public transportation when accompanied by another	1
4. Completely unable to shop	0	4. Travel limited to taxi or automobile with assistance of another	0
		5. Does not travel at all	0
C. Food Preparation		G. Responsibility for Own Medications	
1. Plans, prepares and serves adequate meals independently	1	1. Is responsible for taking medication in correct dosages at correct time	1
2. Prepares adequate meals if supplied with ingredients	0	2. Takes responsibility if medication is prepared in advance in separate dosage	0
3. Heats, serves and prepares meals, or prepares meals, or prepares meals but does not maintain adequate diet	0	3. Is not capable of dispensing own medication	0
4. Needs to have meals prepared and served	0		
D. Housekeeping		H. Ability to Handle Finances	
1. Maintains house alone or with occasional assistance (e.g. "heavy work domestic help")	1	1. Manages financial matters independently (budgets, writes checks, pays rent, bills, goes to bank), collects and keeps track of income	1
2. Performs light daily tasks such as dish washing, bed making	1	2. Manages day-to-day purchases, but needs help with banking, major purchases, etc.	1
3. Performs light daily tasks but cannot maintain acceptable level of cleanliness	1	3. Incapable of handling money	0
4. Needs help with all home maintenance tasks	1		
5. Does not participate in any housekeeping tasks	0		
Score		Score	
Total score _____			
A summary score ranges from 0 (low function, dependent) to 8 (high function, independent) for women and 0 through 5 for men to avoid potential gender bias.			

**Source:**

Graf C. The Lawton instrumental activities of daily living scale. Am J Nurs. 2008;108(4):52-62.

**Attachment 8: Examples of ARI Duration Calculations****Example 1:** If a participant had:

- ARI start date: 10/11
- RiiQ assessments on his device: 10/11 - 16/11
- ARI Day 3-5 visit: 14/11
- ARI Day 29 visit: 8/12
- New onset or worsening of LRTI or URTI:
  - RiiQ at subject's device: 10/11-11/11
  - Planned visits: 14/11 and 8/12

Then the ARI episode end date is 14/11 (= max [enddate1, enddate2] = max [11/11, 14/11]) and the duration is 5 days. In case the same participant did not had a new onset or worsening during the ARI Day 3-5 visit then the end date would be 11/11 and the duration 2 days.

	ARI start (CE domain)				ARI Day 3-5 Visit	Duration
	10/11	11/11	12/11	13/11	14/11	
1	New onset or worsening	New onset or worsening			New onset or worsening	5 days
2	New onset or worsening	New onset or worsening				2 days

Some additional examples below, given the RiiQ assessments reported by the participants on his/her home device do not reach the actual ARI Day 29 visit date:

	ARI start (CE domain)				ARI Day 3-5 Visit	ARI Day 3-5 Unsch. Visit	Duration
	10/11	11/11	12/11	13/11	14/11	15/11	16/11
1	New onset or worsening	New onset or worsening			New onset or worsening	New onset or worsening	7 days
2	New onset or worsening	New onset or worsening			New onset or worsening		5 days
3	New onset or worsening					New onset or worsening	7 days
4	New onset or worsening						1 day

	ARI start (CE domain)				ARI Day 1 Unsch. Visit	ARI Day 3-5 Visit	Duration
	10/11	11/11	12/11	13/11	14/11	15/11	16/11
1	New onset or worsening	New onset or worsening			New onset or worsening	New onset or worsening	7 days
2	New onset or worsening	New onset or worsening			New onset or worsening		5 days
3	New onset or worsening	New onset or worsening				New onset or worsening	7 days

**Example 2:** If a participant had:

- ARI start date: 1/11
- ARI Day 3-5 visit: 4/11
- ARI Day 29 visit: 29/11
- New onset or worsening of LRTI or URTI :
  - RiiQ at subject's device: 1/11-10/11
  - Planned visits: 4/11 and 29/11

If the participant completed the RiiQ assessments from the 1/11 to the 27/11 then the end date would be 10/11 and the duration 10 days. Whereas, if the participant completed the RiiQ assessments from the 1/11 to the 29/11 or to the 30/11 then the end date would be the 29/11 and the duration would be 29 days.

	ARI start (CE domain)								ARI Day 29 Visit *		Duration
	1/11	1/11	2/11	....	10/11	...	27/11	28/11	29/11	30/11	
1	Comp. RiiQ	Comp. RiiQ	Comp. RiiQ	Comp. RiiQ	Comp. RiiQ	Comp. RiiQ	Comp. RiiQ	Comp. RiiQ			
1	New onset or worsening	New onset or worsening	New onset or worsening	New onset or worsening	New onset or worsening				New onset or worsening		10 days
2	Comp. RiiQ	Comp. RiiQ	Comp. RiiQ	Comp. RiiQ	Comp. RiiQ	Comp. RiiQ	Comp. RiiQ	Comp. RiiQ	Comp. RiiQ	Comp. RiiQ	
2	New onset or worsening	New onset or worsening	New onset or worsening	New onset or worsening	New onset or worsening				New onset or worsening		29 days
3	Comp. RiiQ	Comp. RiiQ	Comp. RiiQ	Comp. RiiQ	Comp. RiiQ	Comp. RiiQ	Comp. RiiQ	Comp. RiiQ	Comp. RiiQ		
3	New onset or worsening	New onset or worsening	New onset or worsening	New onset or worsening	New onset or worsening				New onset or worsening		29 days

\*New onset or worsening at ‘ARI Day 29’ visit is based both on RiiQ collected at the site or by the subject and on the clinical assessments completed at the site.

**Example 3:** If a participant had:

- ARI start date: 1/11
- ARI Day 3-5 visit: 4/11
- ARI Day 29 visit: 29/11
- New onset or worsening of LRTI or URTI:
  - RiiQ at subject’s device: 1/11-28/11
  - Planned visits: 4/11 and 29/11

**Example 3:** If a participant had:

- ARI start date: 11/11
- RiiQ assessments on his device: 15/11 - 16/11
- ARI Day 3-5 visit: 14/11
- ARI Day 29 visit: 8/12
- New onset or worsening of LRTI or URTI:
  - RiiQ at subject’s device: 15/11
  - Planned visits: 14/11

Then the ARI episode end date is 15/11 (= max [enddate1, enddate2] = max [15/11, 14/11]) and the duration is 5 days.

	ARI start (CE domain)			ARI Day 3-5 Visit			Duration
	11/11	12/11	13/11	14/11	15/11	16/11	
1	No RiiQ completed on participants device	No RiiQ completed on participants device	No RiiQ completed on participants device	No RiiQ completed on participants device  New onset or worsening on sites device	New onset or worsening		5 days

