#### **4.4.2.1.3. ARI Episode Duration**

The duration of an ARI episode is defined as: *Last day of symptoms above baseline - start date of ARI + 1*. The ARI Day 1 and ARI Day 3-5 visits are always taken into account for the duration if there is a new onset or worsening of a symptom. The ARI Day 29 is taken into account for the duration only if the RiiQ assessments reported by the participants on his/her home device go up to or exceed the ARI Day 29 visit date (actual date). In this case, ARI Day 29 site assessments occurring after this last RiiQ assessment reported by the participants on his/her home device (actual day) are not taken into account for the duration. End of Season as well as Day 365 and Day 730 visits are excluded when determining ARI end dates. Only URTI and LRTI symptoms from clinical assessment and patient reported outcome will be used in calculating the duration of an ARI episode (Table 8).

Moreover, for ARIs with no new onset or worsening of symptoms, duration will not be calculated.

For calculating the ARI duration, the following rules may be used:

- For all ARIs the start dates are reported in the CRF (=CE.CESTDTC where CETERM=ACUTE RESPIRATORY INFECTION and CE.CECAT= ‘’).

- Then a temporary end date for each ARI is created:
  - In case a participant has multiple ARIs, the temporary end date is set as a day before the start of the next ARI.
  - In case a participant has only one ARI, the temporary end date is set as the day of database cut off (15 May 2020).
- Search between the ARI start date and the temporary end date, for the last date the participant had a new onset or worsening of URTI or LRTI symptoms (Table 8), at the RiiQ assessments completed on his /her device and set it as ‘*enddate1*’.
- If the RiiQ assessments, between the ARI start date and the temporary end date, reported by the participants on his/her home device do not reach the actual ARI Day 29 visit date. Search between the ‘ARI Day 1’ and ‘ARI Day 3-5’ visits (both scheduled and unscheduled), for the last date the participant had a new onset or worsening of URTI or LRTI symptoms (Table 8), at the assessments collected during these visits and set it as ‘*enddate2*’.

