- If the RiiQ assessments between the ARI start date and the temporary end date reported by the participants on his/her home device go up to or exceed the ARI Day 29 visit date (actual date). Search between the ‘ARI Day 1’, ‘ARI Day 3-5’ and ‘ARI Day 29’ visits (both scheduled and unscheduled), for the last date the participant had a new onset or worsening of URTI or LRTI symptoms (Table 8), at the assessments collected during these visits (clinical assessments and RiiQ) or at the participants device at home (RiiQ) during these dates and set it as ‘*enddate2*’.
- The ARI episode end date is defined as the maximum between ‘*enddate1*’ and ‘*enddate2*’.
- And the duration is defined as the *end date – ARI start date + 1*

**Note 1:** in case there is no new onset or worsening after the ARI start date then the ARI end date and the duration are considered missing.

**Note 2:** the start date of the ARI is always the date reported in the CE domain, even if the subject started reporting symptoms only later in the diary.

For example, see [Attachment 8](#)

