**Table 8: Symptoms of LRTI and URTI as per RiiQ or Clinical Assessment**

	RiiQ Term	Clinical Assessment Term (ARI Days 3-5 Clinical Visit)
Symptoms of LRTI	Cough	Cough
	Short of breath	Dyspnea or decreased oxygen saturation* or Shortness of breath
	Coughing up phlegm (sputum)	Sputum production
	Wheezing	Wheezing; rhonchi, rales or other sign of consolidation
		Tachypnea
		Respiratory Effort
Symptoms of URTI	Sore Throat	Nasal discharge
	Nasal congestion	Pharyngitis
		Sinus tenderness

Any midturbinate nasal swab and/or sputum sample taken within 7 days after onset of an ARI episode or during the ARI episode will be allocated to that ARI. In case of 2 consecutive ARI episodes, where the second ARI starts within 7 days after the onset of the first episode and the ARI Day 3-5 sample of the first episode is taken while the second episode is ongoing, then the midturbinate nasal swab and/or the sputum sample will be attributed to both ARIs.

For calculating the duration of an ARI episode, the first day of symptoms above baseline and the last day of symptoms above baseline will be considered. Days with missing symptom assessments during an ARI episode will be considered part of the ARI episode. For more details, refer to Section 4.4.2.1.3.

Note: Shortness of breath and respiratory effort reported at the clinical assessment form will be taken into account for the definition of any ARI disease.

Note: RSV RT-PCR confirmation is defined based on the GeneXpert assay only.

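### Note 1 of SAP Section 4.4.2.1.3 sets the duration of an ARI with symptoms only on its start date to missing, while the same section's formula and Attachment 8 make it 1 day

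*SAP*

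**What the plan says.** Section 4.4.2.1.3 defines the duration as "Last day of symptoms above baseline - start date of ARI + 1". For the home-device questionnaire, the end date comes from this step: "Search between the ARI start date and the temporary end date, for the last date the participant had a new onset or worsening". The start date lies inside that window, and nothing excludes it. The main text withholds a duration in one situation only: "for ARIs with no new onset or worsening of symptoms, duration will not be calculated".

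Note 1, at the end of the same section, reads: "in case there is no new onset or worsening after the ARI start date then the ARI end date and the duration are considered missing".

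Attachment 8 gives worked cases. After Example 1 it adds two tables, introduced by a line that begins "Some additional examples below, given the RiiQ assessments reported by the participants on his/her home device do not reach the actual ARI Day 29". In the first of them, row 4 has a single marked day, the ARI start date of 10/11, and its duration is 1 day.

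This duration feeds the median episode length for the three case definitions (Section 4.4.2.2), for any RSV disease in season 1 (Section 4.4.3.2), and for seasons 2 and 3 and all three seasons together (Section 5.4.1.2). It is also the denominator of RiiQ compliance (Section 4.16).

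**The concern.** An episode that is above baseline on its first day and never again is one day long under the formula and the example, and has no length under the note. Two programmers could each follow the document and deliver different datasets.

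The difference is not neutral. The episodes that Note 1 removes are exactly those at the lowest value that the formula can produce, so the medians would describe only the longer illnesses. Section 1.6 says that the detail in this section was added to make clear how duration was handled in the primary analysis. As it stands, a reader cannot tell from the text which treatment was applied to start-day-only episodes in season 1, or which to apply to seasons 2 and 3.

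**Working it through.** **Inputs.** Dates and stated durations from Attachment 8; the formula, the search step, the main exclusion rule and Note 1 from Section 4.4.2.1.3.

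**Step 1: reproduce the plan's figures** with duration = end date − start date + 1 and the start date included in the search.

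| Attachment 8 case | Calculation (days) | Stated | Under Note 1 as worded |
|---|---|---|---|
| Example 1 | 14 − 10 + 1 = 5 | 5 | 5 |
| Example 1, no symptoms at Day 3-5 visit | 11 − 10 + 1 = 2 | 2 | 2 |
| First additional table, row 1 | 16 − 10 + 1 = 7 | 7 | 7 |
| Row 2 | 14 − 10 + 1 = 5 | 5 | 5 |
| Row 3 | 16 − 10 + 1 = 7 | 7 | 7 |
| **Row 4** | **10 − 10 + 1 = 1** | **1** | **missing** |
| Second additional table, rows 1 to 3 | 7, 5, 7 | 7, 5, 7 | 7, 5, 7 |
| Example 2, RiiQ up to 27/11 | 10 − 1 + 1 = 10 | 10 | 10 |
| Example 2, RiiQ up to 29/11 or 30/11 | 29 − 1 + 1 = 29 | 29 | 29 |
| Last Example 3 | 15 − 11 + 1 = 5 | 5 | 5 |

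Every stated duration is reproduced by the inclusive rule. Note 1 changes one case only, row 4.

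**Step 2: direction.** Removing observations at the minimum cannot lower a median. In the four rows of the first additional table, the median of 7, 5, 7, 1 is (5 + 7)/2 = 6. Without row 4, the median of 7, 5, 7 is 7.

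**Step 3: size.** Let f be the percentage of episodes that are start-day-only. After they are dropped, the reported median sits above all of those f per cent and above half of the remaining 100 − f. It is therefore the f + (100 − f)/2 = 50 + f/2 percentile of all episodes.

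| f, assumed (%) | Percentile reported as the median |
|---|---|
| 0 | 50th |
| 2 | 51st |
| 5 | 52.5th |
| 10 | 55th |
| 20 | 60th |

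The SAP gives neither f nor the distribution of durations, so the shift cannot be put into days.

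**Step 4: compliance.** Section 4.16 divides by the duration, or by the smaller of the duration and 7 or 14 days. With a duration of 1 day, all three denominators are 1. With a missing duration, none is defined as written.

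**The case against.** The best defence is that the intended rule can be recovered. The formula, the search window, the main exclusion rule and the worked example all agree, and Section 4.4.2.1.3 sends the reader to Attachment 8 directly after its notes. Note 1 may be a loose restatement of the main rule, meaning from the start date onward, and nothing in the SAP shows that it was programmed literally. Start-day-only episodes may also be rare: no upper or lower respiratory symptom above baseline may appear on any later home questionnaire or at a later Day 3-5 visit, and mild nasal congestion or a sore throat would be enough. All of this stands. It limits the size of the problem and points to the right repair, but it does not make Note 1 say what was probably meant.

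Three stronger readings are tempting and are not supported.

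- *A vaccine effect is hidden.* A reader might infer that Note 1 drops more short episodes in the vaccine arm and so masks milder breakthrough illness. That needs shares that differ by arm, and the SAP gives none. With equal shares, each arm's median moves to the same percentile of its own distribution.
- *The start of the count also conflicts.* Section 4.4.3.1 says that "the first day of symptoms above baseline and the last day of symptoms above baseline will be considered". Counting the last Example 3 from its first recorded symptoms on 14/11 would give 15 − 14 + 1 = 2 days, where Attachment 8 says "and the duration is 5 days". But Section 4.4.3.1 goes on to count days without an assessment as part of the episode, and 11/11 to 13/11 are such days. It then defers to Section 4.4.2.1.3, whose Note 2 fixes the start as the CE-domain date. There is no second contradiction.
- *The plots of AUC against duration are distorted.* Same-day assessments are reduced to the worst score (Section 4.5.1.1), and the Attachment 4 sum begins at the second timepoint. A one-day episode therefore has no terms in its AUC, whatever duration it is given.

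**Conclusion.** The contradiction is real and can be seen on the page: one type of episode has two different durations. It is a wording error in an operative derivation rule. If Note 1 is followed as written, the descriptive ARI-duration medians are unchanged or biased upward, and the affected episodes leave the compliance summaries. The direction is certain. The size rests wholly on the unknown share of start-day-only RSV ARIs and is nil if there are none. Duration is not an outcome in the vaccine efficacy models, and no hypothesis test depends on it.

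**What to change.** In Note 1 of Section 4.4.2.1.3, replace *after* with *on or after*, so that the end date and duration are missing only when no symptom is above baseline from the start date onward. A start-day-only episode then has an end date equal to its start date and a duration of 1 day, in line with the main text of the section and with row 4 in Attachment 8. Section 4.4.3.1 and Attachment 8 need no change on this point.

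The cost is one phrase and a check of the derivation program. Only if the note was coded literally do the duration derivation, the medians and the compliance tables need to be re-run.
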